3.4.6.2 Training of study staff

MCH staff from Mulago (and, if needed, other targeted health facilities) and community support groups will be sensitized to the study objectives, and technical staff including peer educators, counselors, research assistants and study coordinators will be trained in good clinical practices (GCP) and human subject protection (HSP) and use of the study protocol, standard operating procedures (SOPs) and case record forms (CRFs). In addition to the training above, experienced peer educators will also be trained in depth in the use of the *Comprehensive Family Planning and Reproductive Health Training Curriculum* guide. All trained staff will be mentored on a regular basis by on-site investigators, counseling supervisors and the Study Coordinator.

3.5 Study Procedures

Information is provided below and in Appendix I on when each study procedure is to be performed.

Pre-screening:

Study staff may pre-screen potential study participants from the ANC clinic. During these interactions they may explain the study to potential participants and ascertain elements of presumptive eligibility, to be confirmed during screening. These include age of the potentially

eligible participant and her estimated gestational age and lack of diagnosed pregnancy complications. Potentially eligible participants will then be referred to the counselors who will conduct the screening and enrolment procedures, on the same day as the prescreening or a different day depending on how many participants are available on a particular day.

Screening/Enrollment Visit

During the screening and enrolment visit, the participant will provide written consent prior to conducting any screening procedures. Screening for the study involves administering the study eligibility criteria and for participants who do not meet eligibility criteria, screening will be discontinued once ineligibility is determined. Consenting eligible participants will be enrolled and randomized into one of the three arms. The procedures done at the screening and enrolment visit are outlined in the table below.

Table2: Screening/Enrolment Visit

Component		Procedure/Analysis
Administrative: Screening		
 • Eligibility Determination • Obtain written Informed Consent for Screening and Enrolment.
Administrative: Enrollment		
 • Assign Participant ID • Randomization • Update Locator Information • Collect Demographics • Schedule Next Visit • Reimbursement
Behavioral		
 • Baseline Behavioral Questionnaire and ACASI • HIV pre and posttest counseling • Demonstration and Provision of Condoms
Clinical		
 • Collect baseline RH and Medical History • Record any Clinical Events • Perform Clinical Examination (abdominal palpation) • Provide available test results • Provide treatment/referral as appropriate
Laboratory	Blood	 Collect Blood 
  2mls for HIV-1 Serology (rapid tests)  2mls for Syphilis serology RPR (TPAB if positive)
	Urine	 Collect Urine (20mls) 
  Rapid test for Gonorrhea infection  Rapid test for Chlamydia infection
	Pelvic	
 • Collect vaginal swab for rapid Trichomonas vaginalis testing • Collect swab for Bacterial vaginosis testing (PH, Whiff and Clue cells)

Enhanced Peer Support Education and Counseling (Intervention)	Depending on the group the participant is randomized to, the intervention will be done around 4 weeks after enrolment as this is logistically appropriate for the study. Participants in Arm 2 will be put in homogenous groups (similar gestation, age group and language preference) of 8 – 12 adolescents, while the Arm 3 participants will schedule their individual follow-up visits on the same day as their clinic visits. Participants in the Control Arm will receive routine antenatal, delivery and follow-up services with next study visit at 3 months postpartum
Qualitative component	Participants preselected for the serial IDIs and FGDs will have the baseline interviews and FGDs within 3 weeks of enrolment prior to receiving the intervention

The participant will be provided with an appointment card (usual cards used in the ANC/PNC clinics) however a round colored sticker (different colors for each study arm) will be placed on the card to differentiate the 3 study groups.

STI treatment will be provided for any curable STI diagnosed at screening and in follow-up for the participant and her partner/s in accordance with national treatment algorithms.[33-34] Participants found to be HIV positive (by two separate rapid tests) will not be excluded from this proposed study but will be counseled, encouraged to disclose to their partner/s and will receive PMTCT services including Option B+ with ARV treatment for life as per national guidelines. As part of PMTCT services they will be encouraged to invite their partner/s for HIV C&T and their HIV-exposed infants will be followed up with linkages to ongoing services. Participants with positive syphilis tests will be treated and have repeat testing done per local national guidelines and also at the final visit.

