
*Only at 3 months and study exit (month 9 or 6 for the last participants to enroll), † Pre/posttest counseling and HIV testing done only at 3 months and study exit, ‡ STI lab tests done at study exit and when clinically indicated, ¥done at 36 weeks of gestation for all study groups, ‡ done only at study exit for participants with self-reported consistent condom use

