3.5.4 Clinical Evaluations and procedures

This involves history taking, physical and/or pelvic exams and other evaluations as indicated.

History Taking

- Demographic information is obtained
- Risk assessment during pregnancy to rule out any maternal problems (medical and obstetric history and update this history as appropriate)
- Postpartum, obtain history on any maternal problems (medical, gynecological (including symptoms of STIs) and contraceptive use history and update as appropriate)

Physical Exam:

- General physical exam – signs of anemia, BP, weight, breast
- Obstetric exam during pregnancy
- Additional clinical assessments may be performed at the discretion of the examining clinician in response to symptoms or illnesses present at the time of the exam

Other procedures which shall be done as indicated: prescribe contraceptives, provide available test results and provide treatment/referral as appropriate

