3.5.5 Laboratory Evaluations

- Urine (25mls)
 - Urine dipstick for protein and glucose
 - HCG for pregnancy (5mls)
 - Rapid test for Gonorrhea infection (10mls)
 - Rapid test for Chlamydia infection (10mls) Blood (4mls)
 - 2mls for HIV serology (using national algorithm) [37]
 - Hemoglobin Concentration (Hb) by Hemocue ®
 - 2mls for RPR for syphilis (TPAB if positive)

Throughout the study duration, the total amount of blood collected from each participant will be about 10mls. Pelvic

 - Rapid test for Trichomonas
- Bacterial Vaginosis Testing – PH, Clue Cells, whiff test and homogenous abnormal vaginal discharge.

Bacterial vaginosis will be diagnosed using the following Amsel criteria. The presence of three of the following four criteria provides sufficient evidence for a clinical diagnosis of BV.

 - a) Vaginal pH >4.5 ((normal range 3.8 to 4.5)
 - b) The presence of clue cells (bacterial clumping upon the borders of epithelial cells) on wet mount examination. Clue cells should constitute at least 20% of all epithelial cells (an occasional clue cell does not fulfill this criteria).
 - c) Positive amine, "whiff" or "fishy odor" test (liberation of biologic amines with or without the addition of 10% Potassium Hydroxide (KOH)).
 - d) Homogeneous, nonviscous, milky-white discharge adherent to the vaginal walls
- Vaginal fluid for testing presence of Y chromosomes sequences. This is to validate women sexual behavior reporting whether there was unprotected sex in last 14 days.

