3.6 Study Endpoints

3.6.1 Quantitative data outcomes

Primary outcomes

1. Incidence of one or more STIs during study follow-up, with STIs confirmed by laboratory tests of HIV-1, Neisseria Gonorrhoea, Treponema pallidum (Syphilis), Chlamydia trachomatis, Bacterial Vaginosis or Trichomonas vaginalis (Composite outcome)
 - New HIV-1 diagnosis by 2 separate HIV tests with negative HIV-1 test at enrollment AND/OR
 - New Neisseria Gonorrhoea, Treponema pallidum (Syphilis), Chlamydia trachomatis, Bacterial Vaginosis or Trichomonas vaginalis test having been negative at enrollment OR with completed treatment if positive at baseline
2. Reported (and validated) consistent condom use and uptake of effective contraceptive method (Composite outcome)
 - Absence of repeat pregnancy (diagnosed by rapid urine pregnancy testing for HCG)
 - Uptake of effective contraceptive method with insertion/prescription by clinic staff from 3 months postpartum to 9 months or study completion (which ever comes 1st)
 - Self-reported consistent use of condoms during penetrative anal or vaginal sex including a) since enrollment b) since last visit c) at last penetrative sex act
 - Absence of Y-chromosome in analysis of vaginal swabs

Secondary outcomes

3. Acceptability/desirability of assigned clinic service model

Acceptability of clinic service model (composite)

- Frequency of visits
- Relevance of information to own life
- Sense of psychosocial support

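### Arm-coloured stickers on the usual clinic card can show allocation to clinic staff whose prescribing counts in a primary outcome, and the plan masks no assessor

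*Combined protocol and SAP*

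**What the plan says.** The text after Table 2 in section 3.5 gives each participant an "appointment card (usual cards used in the ANC/PNC clinics"), and states that "a round colored sticker (different colors for each study arm) will be placed on the card" so that the three groups can be told apart. Showing the arm is thus the sticker's declared purpose, and the card is the ordinary clinic card.

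Three other places connect clinical staff to the primary outcomes:

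- **Contraception.** Section 3.6.1 lists as a component of the dual-protection composite: "Uptake of effective contraceptive method with insertion/prescription by clinic staff".
- **STI testing.** The footnote to Table 3 (3.5.1) reads "STI lab tests done at study exit and when clinically indicated". Section 3.5.4 adds: "Additional clinical assessments may be performed at the discretion of the examining clinician". The STI outcome in 3.6.1 counts any new infection during follow-up, and 3.7.2 analyses it by Kaplan-Meier, log-rank and Poisson methods.
- **BV.** Section 3.5.5 uses the Amsel criteria: "The presence of three of the following four criteria provides sufficient evidence for a clinical diagnosis of BV". The four are pH, clue cells, amine odour and appearance of the discharge. BV alone is enough to meet the STI composite.

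Section 3.4.6.2 says that maternal and child health staff at the facilities will be made aware of the study objectives. Nowhere does the plan say that a prescriber, examiner, laboratory reader or outcome assessor is kept unaware of the arm.

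**The concern.** Participants and peer educators cannot be blinded to peer support. The staff who prescribe, test and read results at the facilities are in a different position: nothing in the intervention requires them to know the arm, and all three arms receive routine care at the same kind of clinic (3.4.6). A sticker that shows the arm each time the card is presented, to staff who have been told what the study is about, opens a route by which an expectation can become a recorded difference.

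The direction is not fixed. More prescribing to women in the peer-support arms, or fewer BV calls among them, would favour the intervention. More indicated testing in those arms would find more infections and work against it. At stake is whether a difference in either primary outcome, or its absence, can be read as the effect of peer support.

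**Working it through.** **1. How each route stands in the text**

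| Route | Link to a primary outcome | Does the text place these staff with the card? |
|---|---|---|
| Contraception | Insertion or prescription by clinic staff is a component (3.6.1) | Best supported: the outcome definition names clinic staff, and 3.4.6 refers interested intervention participants to the family planning clinic |
| Indicated STI tests | Any infection during follow-up counts (3.6.1); pre-exit tests are discretionary (Table 3 footnote, 3.5.4) | Possible: the person who orders the test is not named |
| BV | One of six infections, sufficient alone (3.6.1) | Possible: the reader is not named |

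**2. The plan's sample size, to fix the denominators**

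Inputs from 3.7.1: 20% control against 10% and 8%; 80% power; 5% type 1 error (sidedness not stated); 10% loss; 215 + 152 + 152 = 519. The ratio is r = 152/215 = 0.707.

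n(control) = [zα√((1+1/r)p̄(1−p̄)) + zβ√(p1(1−p1)+p2(1−p2)/r)]² / (p1−p2)², with p̄ = (p1+r·p2)/(1+r), then divided by 0.90.

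- One-sided 5%, 20% against 10%: 192 and 136 evaluable, inflated to 214 + 152 + 152 = 518. This matches.
- Two-sided 5%, 20% against 9% (the stated average 55% reduction): 219 + 156 + 156 = 531. This is close.
- Two-sided 5%, 20% against 10%: 273 + 194 + 194 = 661. This does not match.

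The unstated sidedness is a separate matter. For what follows, evaluable numbers are 0.90 × 215 = 193.5 and 0.90 × 152 = 136.8.

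**3. Effect of a recorded shift when there is no true effect**

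The shift sizes are assumptions; the documents give none. The 20% is the plan's prevalence at last follow-up, used here as a stand-in for the proportion with any infection.

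SE = √(p1(1−p1)/193.5 + p2(1−p2)/136.8); rejection rate = Φ(−1.96 + δ/SE) + Φ(−1.96 − δ/SE).

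For 20% against a recorded 17%: SE = √(0.16/193.5 + 0.1411/136.8) = √(0.000827 + 0.001031) = 0.0431; δ/SE = 0.03/0.0431 = 0.696; Φ(−1.264) + Φ(−2.656) = 0.103 + 0.004 = 0.107.

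| Outcome | Recorded rates | SE | δ/SE | Two-sided rejection |
|---|---|---|---|---|
| STI | 20% v 19% | 0.0442 | 0.226 | 5.6% |
| STI | 20% v 18% | 0.0437 | 0.458 | 7.4% |
| STI | 20% v 17% | 0.0431 | 0.696 | 10.7% |
| STI | 20% v 15% | 0.0419 | 1.192 | 22.2% |
| Dual protection | 10% v 13% | 0.0359 | 0.835 | 13.3% |
| Dual protection | 10% v 15% | 0.0374 | 1.338 | 26.7% |

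A pooled-variance test changes little (5.5% and 7.2% for the first two rows).

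**4. Effect in the other direction**

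Suppose the true rates are 20% and 10%, and extra indicated testing raises the recorded intervention rate to 12% or 14%. By the same formula, power falls from 74% to 52% or 31%. With the pooled-variance test the figures are 70%, 48% and 29%.

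**5. What a dual-protection shift would require**

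The composite also needs consistent condom use, no repeat pregnancy and no Y-chromosome. If a share s of women met those other components (an assumption), a 5-point shift in the composite needs a prescribing shift of 5/s points among them: 5/0.30 = 16.7 points if s is 30%, and 5/0.60 = 8.3 points if s is 60%.

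**The case against.** The strongest reply is that the sticker adds little to what staff would know anyway. Arms 2 and 3 alone have visits at 36 weeks, around birth and at 6 and 10 weeks postpartum (3.1); the control arm's next study visit after enrolment is at 3 months (Table 2), so the dates on a card would hint at the arm. Sessions are held in different places by arm (3.2.1, 3.4.6), and the participant opens her own envelope (3.4.5). Section 5.2.1 lists STI tests, clinical examination and provision of contraception as study procedures, and study staff who schedule visits would know the arm without a sticker. All of this stands: an arm-neutral card would not by itself mask anyone. What remains is that group sessions are held at the MU-JHU premises and antenatal individual sessions in a separate clinic space, so a prescriber in the family planning clinic would often have to ask, whereas the sticker tells her at once.

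The routes are also narrower than they first look. STI tests at exit are mandatory in every arm, so discretion affects only earlier detections. BV needs three of four criteria, of which pH has a numeric cut-off and clue cells a 20% threshold, so odour and discharge alone cannot make the diagnosis. The other infections rest on serology or rapid tests, which leave less room for judgement. Family planning counselling and referral are part of the intervention, so more prescribing in Arms 2 and 3 is partly the intended effect.

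A reader might infer that the plan gives the arm to laboratory staff and to whoever orders tests or reads BV. The documents do not support that: they do not name these people or say that the card travels with specimens, and 3.8 says participants are identified mainly by study number.

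**Conclusion.** The point holds in a limited form. A stated procedure exposes allocation on the ordinary clinic card, with no masking of any assessor described. The exposure is well supported for staff who prescribe contraception, and only possible for those who order indicated STI tests before exit or judge BV.

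The size and direction of any bias are unknown. With no true effect, 20% in control and 90% of 215 and 152 evaluable, a 3-point shift in the recorded STI rate gives a two-sided false-positive rate of about 11%, and a 1-point shift under 6%. Extra indicated testing would instead cost power. These figures rest on assumed shifts and a simple two-proportion test in place of the planned time-to-event and Poisson models.

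Two stronger readings should be resisted. One is that the sticker itself inflates the error rate by these amounts: no part of an assumed shift can be attributed to the card rather than to the other disclosures. The other is that removing it would blind staff: venue, visit schedule and participants' own knowledge would still show the arm to many. This is a cheap improvement, not a defect that invalidates the design.

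**What to change.** - In 3.5, replace the arm colours with one identical study sticker carrying the participant ID, and keep the arm on the coordinator's list for routing to sessions.
- Label specimens and result forms with ID and visit only.
- In 3.5.5, name who reads the rapid tests and the BV components (pH, whiff test, clue cells), and state that this person is not told the arm.
- In 3.7.2, add a sensitivity analysis of the STI outcome without BV and without infections found only by indicated testing. It should supplement the main analysis, since it also drops real infections that were found and treated before exit.
- Acknowledge that venue, visit schedule and participants' knowledge still disclose the arm, so staff unblinding is reduced but not eliminated.

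The cost is different stickers, a few sentences and one extra analysis; no added staff or tests. The downside is that session staff must look up the arm on a list. This carries a small risk of misrouting, which matters somewhat in services that section 1.1 describes as crowded and if several facilities recruit.

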3.5.1 Follow-up and Study Exit Visits

3.5.1.1 Every month after enrolment during pregnancy through delivery and at 6, 10 and 14 weeks and 6 and 9 months postpartum

During follow-up the study procedures and STI screening tests will be done as summarized in the table below.

Table 3: Week 36 Antepartum, Delivery, Week 6 and 10, Month 3, 6 and 9 Postpartum

Component	Procedure/Analysis
Administrative and Regulatory (all visits including delivery contact for intervention groups)	
 Review/update locator information Provide reimbursement for study visit* Schedule next visit
Behavioral (at 3, 6 and 9 months)	
 Conduct behavioral assessment HIV pre- and post-test counseling†
Clinical (at 36 weeks Antepartum, and as indicated)	
 Review and update RH and Medical History Perform Clinical Examination‡ Prescribe/provide preferred contraceptive method Provide available test results Provide treatment/referral as appropriate

Laboratory	Blood	 Collect Blood  2mls for HIV-1 Serology (rapid tests)†  2mls for Syphilis serology RPR (TPAB if positive)
	Urine	 Collect Urine (20mls)  Rapid test for Gonorrhoea infection  Rapid test for Chlamydia infection  Urine for Protein and glucose¥
	Pelvic	
 • Collect vaginal swab for rapid Trichomonas vaginalis testing • Collect swab for Bacterial vaginosis testing (PH, Whiff and Clue cells) • Collect vaginal swab for testing presence of Y chromosome ‡
Enhanced Peer Support Education and Counseling (Intervention) (at 6, 10 and 14 weeks ,6 and 9 months)		
Depending on the group the participant is randomized to, the intervention will be done ± 2 weeks at all scheduled study visits. This is to allow flexibility in scheduling the sessions for the intervention groups
 
Participants in the Control Arm will have the routine care provided to postpartum in the postnatal clinic

Qualitative component		
Participants preselected for the serial IDIs and FGDs will have the final interviews and FGDs within 2 weeks of the scheduled final education and support session at study exit.
 
In addition, single IDIs will be conducted for participants who

		
seroconvert, have ≥ 2 STIs or have recurrent pregnancy at any time during follow-up.


*Only at 3 months and study exit (month 9 or 6 for the last participants to enroll), † Pre/posttest counseling and HIV testing done only at 3 months and study exit, ‡ STI lab tests done at study exit and when clinically indicated, ¥done at 36 weeks of gestation for all study groups, ‡ done only at study exit for participants with self-reported consistent condom use

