We will conduct a 3-arm, randomized, controlled trial of 519 pregnant adolescents aged 15 through 19 years at enrollment to test the acceptability and effectiveness of two enhanced adolescent friendly reproductive health prevention interventions versus current routine care. In each intervention group, 152 adolescent mothers will be randomized to either the enhanced group peer support education and counseling intervention or to the enhanced one-to-one (individual) peer support education and counseling group with a young, model, peer educator trained to deliver RH education and counseling messages, beginning during pregnancy (≥ 28 weeks) and followed up to 9 months postpartum or study end at or after 6 months (whichever comes first). The control group will consist of 215 adolescent mothers randomized to routine care as provided at Mulago hospital (or the designated health facility) where midwives deliver group sessions during antenatal and postpartum care visits as well as standard PMTCT services including routine opt-out HIV C&T and availability of partner C&T. Syphilis testing should also be routinely provided and treatment provided for infected pregnant mothers and their partners as per local standard of care.

The 3 groups will be enrolled with study visits at 3, 6 and 9 months post-partum however the intervention groups (Arms 2 and 3) will have additional visits at 36 weeks Antepartum, delivery, 6 and 10 weeks postpartum, Quantitative baseline data will be collected on routine demographic characteristics, reproductive history, pregnancy intentions and sexual risk/perceptions and HIV/STI status.

Summarized table 1 of the study schedule and evaluation

	SCR/ ENR	36 weeks APT	Birth†	6 weeks PPT	10 weeks PPT	3 months PPT	6 months PPT	9 months PPT†
Arm 1– Routine Care	X					X		X
Intervention: Enhanced Counseling Education Sessions/Routine care as provided	X			X	X	X	X	X
Behavioral Assessments using IAQ and ACASI	X				X		X	X
Psychosocial Assessment	X					X		X
Obtain/review and update RH and Medical History	X	X	*	*	*	*	*	X
Clinical Examination – Blood Pressure, Weight, Obstetric exam	X	X						
Prescribe contraceptives				X	*	*	*	*
Provide available test results	X	X		*	*	X	*	X
Provide treatment/referral as appropriate	*	*	*	*	*	*	*	*
LABORATORY								
Blood	HIV-1 Serology (rapid tests)	X					X	X
	Syphilis serology RPR (TPAB if positive)	X				€		X
Urine	Protein and Glucose	X	X					
	Rapid test for Gonorrhoea infection	X	*		*	*	*	X

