3.5.2 Behavioral Evaluations

Behavioral evaluations assessed by ACASI and interviewer administered questionnaires include;

- Frequency of unprotected sex (self-report of penetrative sexual intercourse since previous visit)/report of condom use
- Risk behaviors – including any new sexual partners/ encounters, concurrent sexual partners (stable or casual), alcohol/drug use, domestic violence e.t.c.
- HIV/STI risk perception and motivation to utilize RH and pregnancy related services
- Reproductive intentions and family planning
- Male partner/s involvement – presence, cohabitation, economic, psychosocial support, health care support, gender based violence etc

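### Table 1 and Appendix B put the IAQ/ACASI at 10 weeks, where controls have no visit, while Table 3 puts it at 3 months, where every arm attends; the schedules must be reconciled so that condom use is assessed alike in all arms

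*Combined protocol and SAP*

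**What the plan says.** Three tables time the behavioural assessment.

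- Table 3 (Section 3.5.1) covers all follow-up visits from 36 weeks antepartum onwards, including week 10, but limits this component: "Behavioral (at 3, 6 and 9 months)".
- Table 1 (Section 3.1) has a row "Behavioral Assessments using IAQ and ACASI" marked at enrolment, 10 weeks, 6 months and 9 months. The 3-month cell is empty.
- Appendix B has the same row with the same marks.

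Control visits are given in three places.

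- The text of Section 3.1: "The 3 groups will be enrolled with study visits at 3, 6 and 9 months post-partum". It continues that "the intervention groups (Arms 2 and 3) will have additional visits at 36 weeks Antepartum, delivery, 6 and 10 weeks postpartum".
- Table 2 (Section 3.5): "Participants in the Control Arm will receive routine antenatal, delivery and follow-up services with next study visit at 3 months postpartum".
- The row "Arm 1– Routine Care" in Table 1 marks enrolment, 3 months and 9 months, with nothing at 6 months.

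Section 3.5.2 lists among the ACASI and interviewer-administered items: "Frequency of unprotected sex (self-report of penetrative sexual intercourse since previous visit)/report of condom use". Section 3.6.1 makes self-reported consistent condom use, including use since the last visit, part of the condom and contraception composite. Section 3.7.2 compares that composite at the last follow-up. Objective 2.3 (Section 2) compares uptake of dual methods by arm over follow-up.

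**The concern.** Two incompatible schedules exist for one instrument, and the choice between them does not fall equally on the arms. Under Table 3 the first postpartum assessment is at a visit that all three arms attend. Under Table 1 and Appendix B it is at a visit that belongs to Arms 2 and 3 only. Staff using either of those tables would see each control at 3 months without giving the questionnaire.

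Three things are at stake. The number of sensitive-behaviour assessments would differ by arm, in an unblinded trial where self-report feeds a primary outcome. Reports covering the time since the last visit would be collected on different schedules by arm. Any early comparison of dual-method use under Objective 2.3 would have no control side. In addition, Section 3.6.1 counts contraceptive uptake from 3 months postpartum, so a 10-week assessment falls before that window opens, whereas Table 3's first assessment falls at its start.

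**Working it through.** The plan states no figure to reproduce; the check is a count of marked cells. The behavioural and Arm 1 rows of Table 1 each have eight cells for eight visit columns, and the Appendix B behavioural row has the same pattern, so the mismatch is not a shifted column.

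| Source | Enrolment | 10 weeks | 3 months | 6 months | 9 months |
|---|---|---|---|---|---|
| IAQ/ACASI, Table 1 and Appendix B | yes | yes | no | yes | yes |
| Behavioural component, Tables 2 and 3 | yes | no | yes | yes | yes |
| Arm 2/3 visits, text of 3.1 | yes | yes | yes | yes | yes |
| Control visits, text of 3.1 | yes | no | yes | yes | yes |
| Control visits, Table 1 Arm 1 row | yes | no | yes | no | yes |

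Assessments received after baseline = visits marked for the instrument that the arm also attends.

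**Exit at month 9, Table 1/Appendix B followed**
- Arms 2 and 3 (152 + 152 = 304 women): 10 weeks, 6 months, 9 months = 3.
- Controls (215), visits by the text of 3.1: 6 and 9 months = 2.
- Controls, visits by the Arm 1 row: 9 months = 1.

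**Exit at month 9, Table 3 followed**
- Arms 2 and 3: 3, 6 and 9 months = 3.
- Controls by the text of 3.1: 3, 6 and 9 months = 3.
- Controls by the Arm 1 row: 3 and 9 months = 2.

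**Exit at month 6** (allowed for the last women enrolled)
- Table 1/Appendix B: Arms 2 and 3 have 10 weeks and exit = 2; controls have exit only = 1.
- Table 3: 3 months and exit = 2 in every arm.

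So equal counts at month 9 need both corrections: the behavioural row must follow Table 3, and the Arm 1 row must carry the 6-month visit. With the first alone, a site using the Arm 1 row would still have 3 against 2.

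**Who would lack a postpartum record.** Under Table 1/Appendix B with the visits in the text of 3.1, controls lost between 3 and 6 months attend a postpartum visit but have no postpartum IAQ/ACASI. With the Arm 1 row, the same is true of controls lost between 3 months and exit. The documents do not give the number lost in either interval.

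**Recall since the last visit.** Under the text of 3.1 all arms attend at 6 and 9 months, so the 9-month report covers the same interval in each. Under the Arm 1 row the control report at 9 months reaches back to 3 months, while the Arm 2/3 report reaches back to 6 months.

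**The case against.** The strongest reply is that the main analysis is barely touched. Section 3.7.2 compares the composite at the last follow-up, and every version of the schedule includes an exit assessment for all arms. This stands. A reader might infer that the primary comparison is compromised; the documents do not support that. One qualification remains: last follow-up is not defined. If it meant the last visit actually attended, a control last seen at 3 months would have no postpartum condom data, while an intervention woman last seen then would have a 10-week record.

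Other replies also limit the point.

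- A reader might take the planned 10% loss (0.10 × 215 = 21.5, about 22 controls) as the number without postpartum data. That is all planned control loss at any time. It includes women lost before 3 months, for whom neither schedule yields a record, and, under the text of 3.1, women lost after 6 months, who would have one. It is only a ceiling.
- A reader might infer that the loss-to-follow-up weights would be built on unequal data. Section 3.7.2 names no behavioural covariate for them, so this is not an error in the plan.
- It is too strong to say that controls would have no early data of any kind. Section 3.5.3 and Table 1 place a psychosocial assessment at 3 months, although Appendix B omits that mark. Section 3.3.3 gives 4 controls a 10-week serial interview with behavioural forms. Neither replaces the condom items for the whole arm.
- Appendix B read alone has no control row and restricts only the birth contact, so the gap appears only when it is read with Section 3.1 and Table 2. That is true, but those passages are explicit.
- Arms 2 and 3 already receive repeated counselling, so one extra questionnaire may add little to reporting differences. The documents give no size either way.

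None of this removes the contradiction between the tables.

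**Conclusion.** The point holds as a schedule contradiction with a by-arm consequence. If Table 1 or Appendix B governs, post-baseline IAQ/ACASI assessments to month 9 are 3 in Arms 2 and 3 against 2 or 1 in controls. Controls then have no arm-wide behavioural record before 6 months, or before exit, and Objective 2.3 has no early control data. If Table 3 governs, with the visits in the text of Section 3.1, the arms are equal at 3 each.

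This rests on the 10-week visit being for Arms 2 and 3 only, as Section 3.1 states and Table 2 implies for controls ("with next study visit at 3 months postpartum"). The effect on the exit comparison is limited, on the assumption that last follow-up means the exit visit. The number of controls left without a postpartum record cannot be derived from the documents. The point should be corrected, but it does not put the primary comparison in doubt.

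**What to change.** Amend the behavioural row of Table 1 and Appendix B to match Table 3: IAQ/ACASI at 3, 6 and 9 months in all arms, in addition to enrolment. Add the 6-month mark to the Arm 1 row of Table 1 so that it agrees with the text of Section 3.1. If a 10-week assessment is kept in Arms 2 and 3, state that it does not feed between-arm comparisons; the 12 serial-interview participants keep their 10-week interview regardless.

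The cost is one questionnaire added to a control visit that already exists. Against the text of Section 3.1 no visit is added; a site that has been working from the Arm 1 row would need to start seeing controls at 6 months. Using the 3-month values in the loss-to-follow-up weights is an option once they are collected in every arm, but the correction does not require it.
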